8.2.1 Mixed Meal Tolerance Test (MMTT) for glucose and stimulated C-peptide

The mixed meal tolerance test (MMTT) has appropriate sensitivity to detect residual insulin secretion and beta cell function. In the MMTT, following an 8-10 hour overnight fast, a weight-based liquid meal provided as 6 mL/kg (maximum 360 mL) of mixed meal (Ensure Plus, Abbott, see Site Operations Manual), ingested over 5 min with timed blood samples for glucose and C-peptide determination obtained 10 min prior to ingestion ($t = -10$), at baseline ($t = 0$), and at 15, 30, 60, 90, and 120 min after consumption of the liquid meal ([Leighton et al 2017](#)). The time collections for post load samples are based on the start time of the mixed meal.

Blood sample collection will allow measurement of area under the curve (AUC_{0-2 hr}) and peak C-peptide values. MMTT will be collected at baseline, at Weeks 12, 24, 36 and 52 on treatment, and at Week 72 (End of study) visit. The primary efficacy endpoint is the treatment effect on stimulated C-peptide AUC_{0-2 hrs} by mixed meal tolerance test (MMTT) at Week 52 (12 months). Detailed instructions for subjects regarding fasting requirements are summarized in Site Operations Manual.

Proportion of subjects with detectable C-peptide, rate of decline from baseline C peptide; time to undetectable C peptide will be assessed. A timed urine for C-peptide:creatinine ratio will also be assessed as a measure of beta cell function.

8.2.2 Insulin requirements and glycemic control

A key secondary analysis will be to assess partial remission following CFZ533 compared to placebo.

HbA_{1c} is measured as indicated in the Assessment Schedule ([Table 8-1](#)).

Total daily dose of insulin is reported as total daily units of insulin (adding short and long acting preparations) adjusted per body weight (unit/Kg/24 h). This information will be recorded at the site for at least 3 days and up to 7 days prior to each visit, as available (See Site Operations Manual). The average of total daily units of insulin per day (at each visit) will be calculated.

The Insulin Dose Adjusted HbA1c (IDAA1c) is a validated measure to determine beta cell reserve in subjects with T1DM. IDAA1c values ≤ 9.0 correspond to a predicted stimulated C-peptide >300 pmol/L. The formula for IDAA1c is defined as follows: HbA1c (%) + [4 \times insulin dose (units/kg/24 h)] ([Andersen et al 2014](#)). If HbA1c is stated in mmol/mol, it can be converted to percent by the following formula: HbA1c % = (HbA1c mmol/mol \times 0.0915) + 2.15.

Commercially Confidential Information

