Commercially Confidential Information

Commercially Confidential Information

Commercially Confidential Information

Protocol summary

Protocol number	CCFZ533X2207
Full Title	Investigator- and subject-blinded, randomized, placebo-controlled study to evaluate safety, tolerability, pharmacokinetics and efficacy trial of CFZ533 in pediatric and young adult subjects with new onset type 1 diabetes (T1DM).
Brief title	Study of safety and efficacy of CFZ533 in type 1 diabetes pediatric and young adult subjects.
Sponsor and Clinical Phase	Novartis Phase II
Investigation type	Drug
Study type	Interventional
Purpose and rationale	The purpose of this study is to enable the development of CFZ533 in new onset T1DM and to inform the design of subsequent confirmatory studies.
Primary Objective(s)	
 • To evaluate safety and tolerability of CFZ533 in new onset T1DM by assessing adverse events (AEs) and standard safety labs. • To evaluate the treatment effect of CFZ533 on pancreatic beta cell function in new onset T1DM after 52 weeks, by assessing stimulated C-peptide AUC by mixed meal tolerance test (MMTT).
Secondary Objectives	
 • To evaluate the pharmacokinetics (PK) of CFZ533 in new onset T1DM by measuring free CFZ533 plasma concentrations at baseline, during treatment and follow up period. • To evaluate the treatment effect of CFZ533 on full remission by HbA1c $\leq 6.5\%$ (48 mmol/mol) and no exogenous insulin use, or partial remission by insulin dose adjusted HbA1c (IDAA1c) ≤ 9.0 or HbA1c $< 7.0\%$ (53 mmol/mol) with total daily insulin dose of <0.5 units /kg /day, at week 52 in new onset T1DM. • To evaluate durability of effects after washout of CFZ533 on pancreatic beta cell function by assessing stimulated C-peptide AUC by MMTT at week 72 in subjects with new-onset T1DM.

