12.5.1 Efficacy and/or Pharmacodynamic endpoint(s)

Data for the secondary variables (*i.e.* total daily dose of insulin, insulin-dose adjusted HbA1c) will be descriptively summarized for each treatment group and each time point (where applicable).

Full remission will be defined by HbA1c $\leq 6.5\%$ (48 mmol/mol) and no exogenous insulin use, at 52 weeks (1 year). Two validated criteria will be used to assess partial remission including proportion of subjects with (1) Insulin Dose Adjusted HbA1c (IDAA1c) ≤ 9.0 (Mortensen et al 2009) and (2) HbA1c $< 7.0\%$ (53 mmol/mol) and total daily insulin dose < 0.5 units per kg per day (Couper and Donaghue 2009). Stimulated C-peptide AUC by MMTT at Week 72 will be analyzed in the same manner as the primary objective. The baseline*visit interaction term may also be considered for this model due to the follow-up.

The proportion of subjects with detectable C-peptide, rate of decline from baseline C-peptide, and time to undetectable C-peptide will be descriptively summarized with estimates and confidence intervals for each treatment group and each time point (where applicable).

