1.3.2 Secondary objective(s)

Secondary objective(s)	Endpoints related to secondary objectives

To evaluate the pharmacokinetics (PK) of CFZ533 in subjects with new onset T1DM.	
CFZ533 plasma concentrations at baseline, during treatment (Cmax, Tmax after IV administration, and Ctroughs after SC administration) and follow-up period.

To evaluate durability of effects of CFZ533 on pancreatic beta cell function in subjects with new-onset T1DM.	
Stimulated C-peptide AUC by MMTT at 20 weeks from last dose.

To evaluate the treatment effect of CFZ533 on remission or partial remission in subjects with new onset T1DM.	
Not requiring exogenous insulin therapy with HbA1c <6.5% (remission) or Insulin dose adjusted HbA1c (IDAA1c ≤9.0) or HbA1c < 7.0% (53 mmol/mol) and total daily insulin dose <0.5 units per kg per day at 52 weeks (partial remission).

[figure not shown]
Commercially Confidential Information

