4.1 Data analysis general information

Unless otherwise specified: categorical data will be presented as frequencies (n) and percentages. Continuous data will be presented as n, mean, standard deviation (SD), median, minimum, and maximum.

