6.2.2 Descriptive analyses

- For stimulated C-peptide AUC by MMTT at Week 72, total daily dose of insulin, insulin-dose adjusted HbA1c, their change and percent from baseline will be summarized by descriptive statistics for each treatment group and each time point (where applicable).

- The proportion of subjects with remission and each of the three components (full remission and two different criteria for partial remission) and subjects with detectable C-peptide will be descriptively summarized for each treatment group and each time point and overall study period.
- Time to undetectable C peptide will be analyzed by Kaplan-Meier methods by treatment group. Estimates of median time to undetectable C peptide and proportion of subjects with detectable C-peptide and their confidence intervals for each treatment group and each time point (where applicable) will be produced. Time to Peak C-peptide \leq 0.2 pmol/mL (or below LLOQ) and proportion of subjects with C-peptide \geq 0.2 pmol/mL will be analyzed similarly.

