6.2.3 Statistical model, assumptions and hypotheses

Normalized stimulated C-peptide AUC by MMTT at Week 72 will be analyzed in the same manner (and using the same model) as the primary objective. C-peptide AUC at all time points up to and including Week 72 will be included. The baseline by visit interaction term may also be considered for this model.

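### Partial remission versus placebo is announced as a key secondary analysis, but the visible SAP plans no between-arm estimate or interval for remission or for IDAA1c

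*Protocol*

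**What the plan says.** **What is announced.** Protocol 8.2.2 says: "A key secondary analysis will be to assess partial remission following CFZ533 compared to placebo". SAP 1.3.2 gives the objective as "To evaluate the treatment effect of CFZ533 on remission or partial remission in subjects with new onset T1DM". The protocol summary and Protocol Table 2-1 carry the same objective, assessed at Week 52.

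**What is planned for remission.** SAP 6.2.1 defines remission at Week 52 as meeting any of three criteria: full remission, IDAA1c ≤9.0, or HbA1c <7.0% with less than 0.5 units/kg/day of insulin. Under SAP 6.2.2 the proportions meeting the composite and each component "will be descriptively summarized for each treatment group and each time point and overall study period". The default in SAP 4.1 is that "categorical data will be presented as frequencies (n) and percentages". Protocol 12.5.1 defines the criteria as proportions and names no method of comparison.

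**What is planned for IDAA1c.** Values, change and percent change from baseline are summarised by arm (SAP 6.2.2). Arm means are plotted with 80% intervals (SAP 6.2.2.1).

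**Where a secondary model is given.** SAP 6.2.3 is the section for secondary models, and it covers one endpoint: "Normalized stimulated C-peptide AUC by MMTT at Week 72 will be analyzed in the same manner (and using the same model) as the primary objective".

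**The concern.** A treatment effect is a between-arm quantity, and so is a comparison with placebo. A percentage per arm is neither. Other secondary variables are treated more fully: the rate of C-peptide decline has a mixed model with 80% intervals, the detectable-C-peptide and peak-C-peptide outcomes have confidence intervals, and Week 72 C-peptide AUC has the full primary model. The one analysis called key has no contrast.

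The trial exists to inform later confirmatory studies (Protocol 1.2), and Protocol 4.3.1 relies on the secondary endpoints to help show the clinical value of preserving beta-cell function. Both uses need an effect estimate with its precision. With about 12 to 15 placebo subjects, two bare percentages are easy to over-read.

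**Working it through.** **1. The plan's own figure.** The documents give no sample size, power or assumed rate for remission. The only stated power is for the primary endpoint (Protocol 12.8.1), and it fixes the arm sizes: 36 evaluable at 2:1, so 24 and 12.

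- SD of log AUC = sqrt(ln(1 + 0.7²)) = 0.6315.
- Standard error = 0.6315 × sqrt(1/24 + 1/12) = 0.2233.
- Ratio 1.375: ln(1.375)/0.2233 − 1.2816 = 0.145, power 55.8% (55.1% with a t distribution on 34 df), against 55% stated.
- Ratio 1.56: 76.1% (75.4% with t), against 75% stated.
- Dropout: 36/(1 − 0.18) = 43.9, so 44 randomised, about 29 and 15.

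These reproduce, and no stated figure is in dispute.

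**2. How many remission contrasts are needed.** IDAA1c = HbA1c (%) + 4 × insulin dose (units/kg/day).

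- HbA1c <7.0 with dose <0.5 gives IDAA1c < 7.0 + 4 × 0.5 = 9.0.
- No insulin with HbA1c ≤6.5 gives IDAA1c ≤ 6.5 + 0 = 6.5.

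Both criteria lie inside IDAA1c ≤9.0, which is itself the remaining criterion. The any-remission composite is therefore the same set of subjects as IDAA1c ≤9.0, and one difference covers it.

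**3. Precision of that difference.** All remission rates here are assumptions. As a hand check at 40% versus 20%, the 80% Wald half-width is

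- 29:15: 1.2816 × sqrt(0.4×0.6/29 + 0.2×0.8/15) = 0.176
- 24:12: 1.2816 × sqrt(0.4×0.6/24 + 0.2×0.8/12) = 0.196

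For whole-number outcomes, the table gives 80% intervals by two methods. Newcombe combines the two arms' Wilson limits. Miettinen-Nurminen takes the values δ at which (d − δ)/sqrt(V(δ)) = ±1.2816, where d is the observed difference and V uses the proportions fitted under difference δ, times N/(N − 1).

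| CFZ533 | Placebo | Difference | Newcombe 80% | Miettinen-Nurminen 80% |
|---|---|---|---|---|
| 10/24 | 2/12 | 0.25 | 0.04 to 0.41 | 0.04 to 0.42 |
| 10/24 | 3/12 | 0.17 | −0.05 to 0.35 | −0.06 to 0.36 |
| 12/24 | 4/12 | 0.17 | −0.06 to 0.36 | −0.06 to 0.37 |
| 14/24 | 5/12 | 0.17 | −0.06 to 0.37 | −0.06 to 0.38 |
| 12/29 | 3/15 | 0.21 | 0.02 to 0.37 | 0.02 to 0.38 |
| 12/29 | 4/15 | 0.15 | −0.05 to 0.31 | −0.05 to 0.32 |
| 14/29 | 4/15 | 0.22 | 0.02 to 0.38 | 0.01 to 0.39 |
| 17/29 | 6/15 | 0.19 | −0.02 to 0.37 | −0.02 to 0.38 |

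Half-widths are 0.17 to 0.21 by Newcombe and 0.18 to 0.22 by Miettinen-Nurminen. In these examples, observed differences of 15 to 19 points include zero and those of 21 points or more exclude it.

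**4. Power for a true 20-point difference**, one-sided 0.10, normal approximation with a pooled null variance. For 20% versus 40% at 24:12: (0.20 − 1.2816 × 0.1667)/0.1528 = −0.089, power about 46%. With placebo rates of 20% to 40%, power is 44% to 47% at 24:12 and 49% to 52% at 29:15.

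**The case against.** The strongest reply is that description is a reasonable choice here. The trial is labelled non-confirmatory, and power for its primary endpoint is only 55%. Protocol 12.5.1 itself says the insulin-dose and IDAA1c variables will be summarised descriptively, and the SAP follows it. The words calling remission key and compared to placebo sit in an assessment section. Neither statistics section repeats them, and the visible text gives remission no hierarchy, alpha or power. Relabelling one sentence would remove the mismatch.

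Much of that stands. A descriptive plan announced as such would be defensible. It does not remove the point, because the objective is also worded as a treatment effect in both documents.

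A reader might go further and infer three things that the documents do not support:

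- *That the objective cannot be answered.* Counts and percentages by arm let anyone compute the difference and its interval. The comparison is unreported, not lost.
- *That no interval is planned and baseline is ignored.* SAP 6.2.2.1 plans per-arm 80% intervals for mean IDAA1c, and SAP 6.2.2 summarises change from baseline. What is missing is a between-arm, baseline-adjusted estimate.
- *That a formal test was promised and then dropped.* No test or error rate for remission appears in the visible text.

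Redacted text follows Protocol 8.2.2 and SAP 6.2.3.2, and the table shells are a separate document, so a comparison there cannot be excluded. The visible sections where it belongs contain none.

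**Conclusion.** The mismatch is real and inexpensive to close. A comparison with placebo is announced, and the visible plan delivers per-arm description only, for remission and for IDAA1c. This does not affect the primary analysis.

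The size should not be oversold. The precision figures rest on assumed remission rates and on 24:12 to 29:15 subjects. On that basis the 80% interval reaches about 0.17 to 0.22 either side. It would be tempting to infer that a contrast would settle whether a 20-point effect exists. It would not: power for a true 20-point difference is only about 44% to 52%. The gain is an explicit estimate with visible uncertainty. The nesting result needs no rate assumption; it follows from the definitions, provided the same HbA1c and insulin dose feed all three criteria.

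**What to change.** Add to SAP 6.2.3, for the full analysis set at Week 52, both labelled supportive:

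1. The difference in the proportion with IDAA1c ≤9.0 (CFZ533 minus placebo), with an 80% Miettinen-Nurminen interval. State a rule for missing Week 52 status, for example counted as not in remission with an observed-case check. The rule matters because about 18% dropout is planned for. Note that this one difference also covers the any-remission composite.
2. The difference in IDAA1c, adjusted for baseline IDAA1c and age group, with its 80% interval. Use the primary mixed model at the visits where both HbA1c and insulin dose are collected. The treatment-period HbA1c row is not visible in the public assessment schedule, so the SAP should list those visits.

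Label full remission as descriptive. If the sponsor prefers no contrast, the minimum is to reword Protocol 8.2.2 so that remission is descriptive and not a key comparison. That ends the inconsistency but leaves the stated treatment effect unestimated.

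The cost is two outputs from variables already derived, and two further comparisons without multiplicity adjustment.

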8.2.4 Appropriateness of efficacy assessments

- The mixed-meal tolerance test (MMTT) is a standardized, reproducible measure of beta cell function with C-peptide measures to evaluate endogenous residual beta cell function in T1DM in the setting of exogenously administered insulin ([Leighton et al 2017](#)).
- HbA1c is the standard clinical measure of average glycemia. National Glycohemoglobin Standardization Program (NGSP) methodology will be used.

Commercially Confidential Information

8.3 Safety

Safety assessments are specified below with the assessment schedule detailing when each assessment is to be performed.

For details on AE collection and reporting, refer to the AE section (see [Section 10.1.1](#)).

Table 8-2 Safety assessments

Assessment	Specification
Physical examination	
A complete physical examination will include the examination of general appearance, skin, neck (including thyroid), eyes, ears, nose, throat, lungs, heart, abdomen, back, lymph nodes, extremities, vascular, and neurological. Tanner staging will include examination of external genitalia, breast and pubic hair.
 
A short physical exam will include the examination of general appearance, vital signs (blood pressure [SBP and DBP] and pulse), thyroid, skin for injection sites. A short physical exam will be at all visits starting from screening visit except where a complete physical examination is required.
 
Information for all physical examinations must be included in the source documentation at the study site. Clinically relevant findings that are present prior to signing informed consent must be included in the Medical History part of the CRF. Significant findings made after first administration of investigational drug which meet the definition of an Adverse Event must be recorded on the Adverse Event section of the CRF.

Vital signs	
Vital signs include temperature, BP and pulse measurements.
 
For all visits: After the subject has been sitting for five minutes, with back supported and both feet placed on the floor, systolic and diastolic blood pressure will be measured once using an automated validated device and with an appropriately sized cuff including for pediatric use. A single repeat measurement for systolic and diastolic BP can be performed as needed to verify the first measurement and as per the PI's judgment.

Height and weight	Height in centimeters (cm and to the nearest 0.1 cm, without shoes and with the use of a calibrated equipment for subjects < age 18 years) and body weight (to the nearest 0.1 kilogram (kg) in indoor clothing and without shoes) will be measured.

The methods, assessment, specification, and recording for each assessment will be detailed in the Study Operation Manual.

8.3.1 Hypoglycemic events

The American Diabetes Association (ADA) has proposed a definition of hypoglycemia as an event accompanied by a measured plasma glucose concentration ≤ 3.9 mmol/L (70 mg/dL) based on the observed threshold for glucose counter-regulation activation in a non-diabetic population with a lower threshold of 3.9 mmol/L (70 mg/dL) as the definition of clinically relevant glucose levels ([Workgroup on Hypoglycemia, American Diabetes Association 2005](#); [Sequist et al 2013](#)).

While standardized reporting of hypoglycemia is desirable, it has been argued that defining hypoglycemia at a glucose level ≤ 3.9 mmol/L (70 mg/dL) may lead to considerable overestimation of the frequency of clinically relevant hypoglycemia. In a study report with a large cohort of patients it was shown that a threshold level of 3.1 mmol/L (56 mg/dL) would provide a more accurate estimate of the frequency ([Swinnen et al 2009](#)) Continuous glucose monitor (Dexcom) alert and alarm thresholds are set at 54 mg/dL (3.0 mmol/L) and so this proposed cut-off value will be used in the current study to define hypoglycemia events.

Severe hypoglycemia is an event requiring assistance of another person to actively administer carbohydrates, glucagon, or take other corrective actions.

Hypoglycemic data will be classified as defined in [Table 8-3](#). Glycemic thresholds above and below 54 mg/dL (3.0 mmol/L) indicate different degrees of urgency for clinical action: Hypoglycemia with glucose 54 to 69 mg/dL (3.0 to 3.9 mmol/L, often referred to as Level 1 hypoglycemia), is an alert threshold, independent of any acute symptoms, and healthcare professionals and people with diabetes should monitor time spent in this range of hypoglycemia. Hypoglycemia with a glucose level of below 54 mg/dL (3.0 mmol/L, often referred to as Level 2 hypoglycemia), with or without symptoms, is considered clinically significant in that it may trigger counterregulatory responses, cause cognitive impairment leading to severe hypoglycemia, and therefore requires immediate attention.

While hypoglycemic adverse events will follow the classification in [Table 8-3](#), adverse events other than hypoglycemia will follow standard grading mild, moderate, or severe ([Section 10.1.1](#)) grading system.

Hypoglycemia events will be recorded in the study diary which will be reviewed and discussed with the subject at each visit. Hypoglycemia may also be assessed via CCI

data review performed by the investigator, but asymptomatic events do not need to be entered as adverse events when additional treatments are not required. CCI

The investigator will record these events according to the table below under actions taken:

Table 8-3 Recording and classification of hypoglycemia as reported in the Study Diary

Severity	Symptoms	Plasma Glucose ¹	Action Taken	Classification ²
Subject able to initiate self-treatment if necessary	Symptoms suggestive of hypoglycemia	≥ 3.0 mmol/L (54 mg/dL)	Complete the Adverse Event and-Hypoglycemia forms of the eCRF	Pseudo or possible symptomatic hypoglycemia (other causes of symptoms reasonably excluded)
	Symptoms suggestive of hypoglycemia	≤ 3.0 mmol/L (54 mg/dL)	Complete the Adverse Event and-Hypoglycemia forms of the eCRF	Documented Symptomatic Hypoglycemia
	Symptoms suggestive of hypoglycemia	Not taken	Complete the Adverse Event and-Hypoglycemia forms in the eCRF	Probable Hypoglycemia
Asymptomatic		≤ 3.0 mmol/L (54 mg/dL)	Enter on Hypoglycemia form unless detected on CGM ³ (i.e. enter if detected by fingerstick) Confirm glucose value(s) in the study diary, unless detected on CGM.	Asymptomatic Hypoglycemia

Severity	Symptoms	Plasma Glucose ¹	Action Taken	Classification ²
Subject is unable to initiate self-treatment and requires third party assistance or hospitalization	Symptoms suggestive of hypoglycemia	< 3.0 mmol/L (54 mg/dL)	Enter symptom(s) and glucose value(s) in the Adverse Event and Hypoglycemia forms of the eCRF.	Severe Hypoglycemia
	Symptoms suggestive of hypoglycemia	Not taken	Enter symptom(s) in the Adverse Event and Hypoglycemia forms of the eCRF	Suspected Severe Hypoglycemia

1. A plasma glucose level of 3.0 mmol/L (54 mg/dL) corresponds to a whole blood glucose (glucometer data) of about 2.7 mmol/L (49 mg/dL), noting plasma glucose values are about 11% higher than those of whole blood when the hematocrit is normal.
2. The classification of adverse events as hypoglycemic events should be adjudicated by the clinical Investigator.
3. Low glucose values that are asymptomatic Commercially Confidential Information do not need to be entered into the Hypoglycemia form. If the subject is not using CGM and the low glucose value is detected by alternate means (*i.e.* fingerstick or serum/plasma) then the asymptomatic hypoglycemic event should be captured on the Hypoglycemia form.

